#### **Interventions and Duration**

This study will compare the outcomes of PFDD vs PFD. The study will occur over a five year period. The enrollment period will last for two years and 8 months. Data collection for each participant is for the primary analysis is to be one year and will be structured in the following manner:

- Pre-operative (the initial outpatient neurosurgery visit prior to decompression) including CHIP & HUI-3 QOL questionnaire
- Intra-operative
- Post-Operative
- <6 weeks post-operation including CHIP & HUI-3 QOL questionnaire
- 3-6 months post-operation including CHIP & HUI-3 QOL questionnaire
- 12±2months post-operation including CHIP & HUI-3 QOL questionnaire

- Data related to additional outpatient neurosurgery visits that occur during the one year collection period will also be collected.

MRI of the brain and cervical and thoracic spine are required prior to PFD or PFDD. Pre-operative lumbar spine MRI will be left to the discretion of the surgeon. MRI of the cervical and thoracic spine are required 12±2 months post-operatively.

- Imaging not required for study but included for review if available during the 1-year +/- 2 month study collection period:
  - Additional MRIs of the brain or cervical, thoracic, or lumbar spine obtained for the clinical care of the patient, including those performed due to:
    - Revision/redo decompression
    - Syrinx fenestration or syrinx shunt
    - Spinal Fusion
  - CT of the brain or cervical, thoracic, and lumbar spine
  - "Long cassette" or "scoliosis" X-rays and X-rays of the cervical, thoracic, and lumbar spine

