1.2 Secondary Objectives

Specific Aim 2: Determine if PFD provides non-inferior clinical improvement and syrinx regression compared to PFDD.

Hypothesis: Clinical improvement and syrinx regression provided by PFD will be non-inferior compared to those provided by PFDD.

Anticipated Outcome: Clinical symptoms, neurological function, and syrinx regression ≤ 12 months will be non-inferior following PFD when compared with PFDD.

- Rates of revision decompression surgery (PFD or PFDD) and progression of spinal deformity ≤12 months after PFD also will be non-inferior to PFDD. Please note that the time window is ≤12 months. When there are multiple visits within this window, the visit with the closest to 12 months after surgery will be used.
- For this aim, clinical symptoms and syrinx regression ≤12 months will be used as the primary outcome variable. Results based on the rates of revision decompression surgery and progression of spinal deformity will be exploratory.

Corresponding Variable Names for 'Clinical Improvement'

• Outcome – Scores, Limonadi/Binary -> compare for symptoms and neurological deficits

- Timeframe compare preoperative to:
- ≤ 6 weeks
- 3-6 months
- 12 (+/- 2) months (primary)
- Binary Scoring is primary
- Limonadi Scoring specifics:
- Each subject was given a score for each symptom at each visit, 2=resolved, 1=improved, 0=stable, -1 = worse.
- Symptom scores within a patient were then averaged across visits (per Limonadi paper) to get patient-level symptom-specific scores.
- These patient-level symptom-specific scores were then averaged to get a single overall score per patient.
- These single overall scores per patient were then averaged within site randomization to get group comparisons between sites randomized to PFD and sites randomized to PFDD.
- Binary Scoring specifics:
- Each subject was given a binary score for each symptom at each visit, 1=positive outcome, 0=negative outcome.
- Symptom scores within a patient were then averaged across visits (per Limonadi paper) to get patient-level symptom-specific scores.
- These patient-level symptom-specific scores were then averaged to get a single overall score per patient.
- These single overall scores per patient were then averaged within site randomization to get group comparisons between sites randomized to PFD and sites randomized to PFDD.

Symptoms						
	Double Vision					
	Sensory Symptoms					
	Weakness Symptoms					
	Dysphagia					
	Hoarseness					
	Choking					

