4. STUDY INTERVENTIONS

4.1 Interventions, Administration, and Duration

The intervention performed will either be a PFD or PFDD. It will be predetermined, based on cluster randomization, which procedure each center performs on their respective participants. A computer-generated randomization sequence will be generated independently by the study statistician. The surgery will occur in each respective center's operating room. With the exception of uniformly receiving the designated center intervention, all research participants will receive usual clinical care in accordance with institutional practice and judgment. Clinical care will include at a minimum an initial clinical evaluation by a participating pediatric neurosurgeon, surgical treatment (PFDD or PFD) and associated perioperative care, and routine post-operative care with prescribed follow-up clinical assessments at ≤ 6 weeks, 3-6 months, and 12 months (+/-2 months = 10-14 months) after surgery

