The primary outcome is a binomial outcome measured as a surgical complication and/or requirement for reoperation for complication management ≤ 12 (+/- 2 months) months after initial PFDD or PFD. To account for within cluster correlation, possibly variable cluster size and the relatively small number of clusters in this cluster randomized trial, generalized estimating equations (GEE) with small-sample correction or random effect logistic regression will be used for the primary analysis of this cluster randomized trial [35, 36].

Specifically, a GEE model with a logit link function and adjustment for baseline covariates can be expressed as follows:

$logit(\pi_{ij}) = \mu + \delta T_i + x_{ij}\beta$

where $T_i = I$ if group *i* is assigned PFD and 0 otherwise. Accordingly, δ is the intervention effect. Let x_{ij} is the p-dimensional vector of group-level of individual level covariates from individual *j* (*j* = 1, ..., n_i) nested in center *i* (*i* = 1, ..., # of active centers here); and β is the vector of covariate effects. Also let the outcomes (CSF-related complication ≤ 6 months, yes/no) are independently distributed as $y_{ij} \sim \text{Bernoulli}(\pi_{ij})$. Further let, μ be the log-odds of positive outcome ($y_{ij} = 1$) for PFDD subjects with reference values for covariates ($x_{ij} = 0$) and average random effect ($\gamma_i = 0$). The exchangeable correlation structure will be used for the within-group homogeneity for the correlation structure of the outcomes. Note that, this correlation parameter corresponds to the intraclass correlation coefficient (ICC).

Specific Aim 2:

Hypothesis: Clinical improvement and syrinx regression provided by PFD will be non-inferior compared to those provided by PFDD.

Anticipated Outcome: Clinical symptoms, neurological function, and syrinx regression ≤ 12 months (± 2 months) provided by PFD will be non-inferior compared to those provided by PFDD. The non-inferiority margin is defined as the difference between the outcome rates by treatment. For the clinical improvement outcome, a non-inferiority margin of 0.17 units will be used. A non-inferiority margin of 0.135 units will be used for the syrinx regression outcome.

Clinical symptoms, neurological function, and syrinx regression are defined as rates of change from baseline to 12 months. The 1-sided confidence interval for the difference in rates between the PFD and PFDD groups will be calculated and compared to the corresponding non-inferiority margins.

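### The SAP states the Aim 2 assessment window inconsistently: its visit-selection rule stops at month 12, while the final visit and the only required post-operative MRI are due at 10 to 14 months

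*SAP*

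**What the plan says.** SAP section 1.2, under Specific Aim 2, gives an explicit instruction: "Please note that the time window is ≤12 months". The next sentence is the selection rule: "When there are multiple visits within this window, the visit with the closest to 12 months after surgery will be used". Both stand in the bullet on revision surgery and spinal deformity. The bullet after it carries the same ceiling to the main endpoints: "clinical symptoms and syrinx regression ≤12 months will be used as the primary outcome variable".

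Other places use a different window:

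- SAP section 1.2, time frame for clinical improvement: "12 (+/- 2) months (primary)".
- SAP section 7.4 places syrinx size and spinal alignment at 12 ± 2 months.
- SAP section 7.5, Aim 2: "Clinical symptoms, neurological function, and syrinx regression ≤ 12 months (± 2 months)". The next paragraph says that these outcomes "are defined as rates of change from baseline to 12 months".
- SAP section 4.1 sets the final clinical assessment at "12 months (+/-2 months = 10-14 months) after surgery".
- Protocol, Interventions and Duration: "MRI of the cervical and thoracic spine are required 12±2 months post-operatively". SAP section 2 agrees, and no earlier post-operative MRI is required.

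For Aim 3, SAP section 1.2 also uses the label of up to 12 months, but section 7.5 then ties the primary analysis to exams done between 10 and 14 months. Aim 2 has no equivalent sentence.

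**The concern.** Two analysts who follow this SAP in good faith could build different Aim 2 data sets. One would stop at month 12. The other would accept everything from month 10 to month 14. Clinical symptoms and syrinx regression are the two outcomes on which the non-inferiority claim rests, so the choice is not a side issue.

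The section 1.2 rule has two faults if applied literally. It has no upper tolerance, so an assessment done on schedule at month 13 is out of window. It has no lower bound, so the assessment closest to month 12 may be a 3-6-month visit or even one within 6 weeks, which describes a different stage of recovery. Syrinx regression is the most exposed outcome, because a patient scanned only at month 13 would have no eligible scan at all.

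**Working it through.** **1. The rules applied to one patient.** Take 30-day months, as the SAP states for the Aim 3 metrics in section 1.2. Month 12 is then day 360, and 10-14 months is days 300-420. Suppose a patient is seen at 5 months (day 150) and 12.5 months (day 375), with the only post-operative MRI on day 375.

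| Rule | Clinical visit selected | Syrinx scan selected |
|---|---|---|
| Up to 12 months, closest to 12 (section 1.2 as written) | day 150 | none |
| 10-14 months, closest to 12 | day 375 | day 375 |

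The patient complied with the schedule in both rows.

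**2. How much of the permitted window is at issue.** (420 − 360) / (420 − 300) = 60/120 = 50% of its length. This is a share of days, not of patients.

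**3. Reproducing the plan's power for syrinx regression.** Inputs from SAP section 7.2.1, Aim 2: 89.1% regression in the PFDD arm, margin 0.135, one-sided alpha 0.05, effective n of 68 per group, stated power 81%. With no true difference between arms:

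SE = √[2 × p(1 − p) / n]; power = Φ(margin/SE − 1.645)

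SE = √[2 × 0.891 × 0.109 / 68] = 0.0534; 0.135/0.0534 = 2.526; Φ(2.526 − 1.645) = Φ(0.881) = 81.1%. The stated figure reproduces.

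**4. Power if post-month-12 scans are excluded.** Let f be the share of patients assessed after month 12. The documents do not give f. Assume that these patients have no earlier scan and are not imputed, so that n = 68(1 − f):

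| f | n per group | Syrinx power |
|---|---|---|
| 0 (12 ± 2 reading) | 68 | 81.1% |
| 10% | 61.2 | 77.4% |
| 25% | 51 | 70.6% |
| 50% | 34 | 55.6% |

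The 50% row corresponds to visits spread evenly over days 300-420, which is an assumption.

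**5. Clinical improvement.** With 78.6%, margin 0.17 and 72 per group, the same formula gives 80.0%, matching the stated 80%. The same proportional losses would give 76.3%, 69.5% and 54.5%, but only if no earlier visit were used. The section 1.2 rule would normally supply one, so for this outcome the likelier effect is a change in what is measured rather than a loss of patients.

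**The case against.** The strongest reply is that the authors meant 12 ± 2 months throughout and used the 12-month ceiling as shorthand. Several things support this. Section 1.2 itself marks 12 ± 2 months as primary for clinical improvement. Sections 7.4 and 7.5 attach the tolerance to syrinx size and to the Aim 2 endpoints. Aim 3 carries the same shorthand and is then analysed at 10 to 14 months. Choosing the visit closest to 12 months also fits a two-sided window better than a hard stop. And the rule sits in a bullet about outcomes that the next bullet calls exploratory.

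This shows that a hard stop at month 12 was probably not intended. It does not remove the conflict. The tolerance in section 1.2 is listed under clinical improvement only. The section 7.5 wording still has no lower bound and is followed by a plain 12-month definition. The one sentence that tells the analyst which visit to take points the other way.

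Four stronger inferences are tempting, and the documents do not support them:

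- *Every assessment after month 12 is discarded.* The passages contradict each other, so this is not established. The planned analysis of follow-up from 6 to 24 months also admits later visits, although it is secondary.
- *Earlier scans are all from patients doing badly.* The protocol admits additional MRIs obtained for clinical care and gives revision, syrinx surgery and fusion as included reasons, not the only ones. Section 6.2.3 lists radiology, if applicable, at both early visits. Selection is possible but not shown.
- *Early or missing outcomes would hide a true difference and favour non-inferiority.* The direction of any bias cannot be read from the documents. Loss of patients alone lowers power, which makes non-inferiority harder to claim.
- *An early visit simply becomes the 12-month symptom score.* Section 1.2 also averages symptom scores across visits, so the effect on that outcome is less direct.

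**Conclusion.** The point holds as an internal contradiction in the Aim 2 window. The section 1.2 rule is wrong as written, because it would exclude assessments that comply with the schedule and could put early ones in their place. Other passages lean towards 12 ± 2 months, but none settles the matter for Aim 2 as section 7.5 does for Aim 3.

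The size is conditional. Under the 12 ± 2 reading the stated powers stand. Under the literal reading, syrinx power depends on a share of late assessments that the documents do not report, and on those patients having neither an earlier scan nor an imputed value. The SAP does plan imputation, so the lower figures illustrate what is at stake and do not forecast it. The need for correction does not depend on them.

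**What to change.** Replace the window and visit-selection sentences in SAP section 1.2 with: *The 12-month outcome is the assessment closest to 12 months among those from 10 to 14 months after surgery (days 300-420 at 30 days per month).*

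Apply it to symptoms, neurological findings, syrinx regression and spinal deformity, and bring the Aim 2 wording in sections 1.2 and 7.5 into line with it. This gives Aim 2 the window that section 7.5 already uses for Aim 3.

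Do not add a new missing-data rule at the same time. Patients with no assessment in the window should follow the existing plan in section 7.5, which compares exclusion, last observation carried forward and Buck's method, and should enter the planned secondary analysis to 24 months.

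The cost is one sentence and two or three matching edits. No new data are needed.

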The non-inferiority margins for this trial were determined in conjunction with a panel of experts on CM+SM and related treatment (the Park-Reeves investigators), our non-physician stakeholder partners, and our patient partners, [name], [name], [name], [name], [name], [name], and [name]. Using a clinical, Delphi-type approach [46] for the complex measure of clinical improvement, the research team agreed upon a non-inferiority margin of no more than 20% lower response for PFD from the PFDD group. The clinical improvement rate (the improvement from baseline to 12 months) for the PFDD group was provided as 78.6% in the Durham study [27]. Thus, with the sample size of 72 subjects per group (after an assumed 2% dropout), we can conclude the non-inferiority of the PFD to PFDD with a margin of 0.17 units (α =0.05, 80% power). This corresponds to clinical improvement rate of 61.6% in the PFD group. It was shown in the Durham study that the clinical improvement following PFD was 64.6%.

Determine if PFD provides non-inferior clinical improvement compared to PFDD (Non-inferiority Design)							
Outcome	PFDD	PFD	Data Source	Non-inferiority Margin	α-level	Subjects per group	Power
Clinical Improvement	44/56 (78.6%)	51/79 (64.6%)	Durham [27]	0.17	0.05	72	80%

For these calculations, the drop-out rate is assumed to be 2%, and the one-sided type I error rate is 0.05.

After determination with the Delphi method, the non-inferiority margin was subsequently confirmed as appropriate using Rothman's 95-95 approach [47, 48] and the FDA guidelines for selecting the non-inferiority margin for non-inferiority clinical trials [49]. Using these methods, the non-inferiority margin was estimated using the effect of the standard treatment (PFDD) from Durham's meta-analysis [27], with the lower 1-sided 95% confidence interval for the random-effects meta-analysis calculated to be used as a non-inferiority margin. When the data from the PFDD group from the Durham study was used for the clinical improvement outcome, the 95% lower 1-sided confidence interval from the random effects model was calculated as 0.611. In our proposal, we defined the non-inferiority margin as the difference between the clinical improvement rates in the PFDD and PFD groups ($\pi_{PFDD} - \pi_{PFD}$). For the clinical improvement outcome, this corresponds to the non-inferiority margin of 0.786 – 0.611 = 0.175 units. Therefore, our

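### The primary Aim 2 clinical-improvement score is a mean share of symptoms, but the 0.17 margin and 72 per group belong to a proportion of patients, and no rule links the two

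*SAP*

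**What the plan says.** **The score (SAP 1.2, Specific Aim 2).** "Binary Scoring is primary" for clinical improvement. It is built in four steps:

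1. "Each subject was given a binary score for each symptom at each visit, 1=positive outcome, 0=negative outcome".
2. "Symptom scores within a patient were then averaged across visits", a step the SAP attributes to a cited paper.
3. "These patient-level symptom-specific scores were then averaged to get a single overall score per patient".
4. The patient scores are averaged by randomised arm to give the group comparison.

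**The time point (SAP 1.2).** The list of time frames marks 12 ± 2 months as primary. The same section also says: "For this aim, clinical symptoms and syrinx regression ≤12 months will be used as the primary outcome variable". Under the item on revision surgery and spinal deformity, it stresses a window of up to 12 months and takes the visit closest to 12 months when there are several.

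**The margin and sample size (SAP 7.2.1, Aim 2 margins and power).** "The clinical improvement rate (the improvement from baseline to 12 months) for the PFDD group was provided as 78.6" per cent, shown in the table as 44 of 56 patients. The margin is 0.17 and the implied PFD rate is 61.6%. There are 72 patients per group, a one-sided alpha of 0.05 and 80% power. A later sentence of the same section calls 0.175 the recommended margin.

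**The test (SAP 7.5, Specific Aim 2).** "Clinical symptoms, neurological function, and syrinx regression are defined as rates of change from baseline to 12 months". A one-sided confidence interval for the difference in rates is compared with 0.17.

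**The concern.** A proportion of patients improved and a mean share of symptoms with a positive score are different quantities, even though both run from 0 to 1. Take a patient with four symptoms, three of them positive. The share is 0.75. As a yes/no response the same patient counts 1 if the rule is at least half positive and 0 if the rule is all positive. A gap of 0.17 on one scale is therefore not in general a gap of 0.17 on the other.

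The margin was argued as a tolerable loss in the proportion of patients who improve. If the arm means of the averaged score are set against it, the result does not answer that question. The verdict can then turn on choices the SAP leaves open: whether a stable item is positive, how a symptom that was never present counts, and which visits enter the average.

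Averaging over visits raises a second issue. Read literally, it mixes early visits into an endpoint whose primary time point is 12 ± 2 months.

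**Working it through.** **1. The plan's own figure.** Inputs from SAP 7.2.1: rate 0.786 in both arms, margin 0.17, one-sided alpha 0.05 (z = 1.645), power 80% (z = 0.842).

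- n per group = 2 × 0.786 × 0.214 × (1.645 + 0.842)² / 0.17² = 0.3364 × 6.183 / 0.0289 = 71.97, so 72.
- Standard error at 72 per group = √(0.3364 / 72) = 0.0684. Power = Φ(0.17 / 0.0684 − 1.645) = Φ(0.842) = 80.0%.
- With 0.175 in place of 0.17, n = 2.080 / 0.0306 = 67.9, so the stated 72 goes with 0.17.

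The variance 0.786 × 0.214 (SD 0.41) is that of a yes/no outcome per patient. The stated 72 is reproduced as a comparison of two proportions of patients.

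**2. What links the score to the proportion.** SAP 1.2 ends in arm means of patient averages and gives no cut-off. SAP 7.2.1 starts from patient counts. SAP 7.5 speaks of rates and does not say when a patient counts as improved. The Protocol (9.4, 9.5, 10.3.3) has no such rule either. No section restates 0.17 for a mean share.

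**3. How much it could matter (illustration, not a bound).** Assumptions: one visit; k = 3, 4, 6 or 8 symptoms per patient; beta-binomial counts with within-patient correlation ρ = 0.3 or 0.6; true responder rates exactly 0.786 and 0.616; 72 per group; no centre effect. For each responder rule, the arm means m₁ and m₂ are solved so that the responder rates hold. The share variance is m(1 − m)[1 + (k − 1)ρ]/k, and P(non-inferior) = Φ((0.17 − (m₁ − m₂))/SE − 1.645).

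Worked case, 'all positive', k = 4, ρ = 0.3: m₁ = 0.913, m₂ = 0.831, gap 0.082. SE = √[(0.913 × 0.087 + 0.831 × 0.169) × 0.475 / 72] = 0.038. P = Φ(0.088/0.038 − 1.645), which is 0.74 with unrounded inputs.

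| k | Half: gap (ρ 0.3 / 0.6) | Half: P(non-inferior) | All: gap (ρ 0.3 / 0.6) | All: P(non-inferior) |
|---|---|---|---|---|
| 3 | 0.152 / 0.166 | 0.09 / 0.06 | 0.096 / 0.125 | 0.53 / 0.20 |
| 4 | 0.158 / 0.176 | 0.08 / 0.04 | 0.082 / 0.116 | 0.74 / 0.27 |
| 6 | 0.150 / 0.171 | 0.10 / 0.05 | 0.067 / 0.104 | 0.93 / 0.37 |
| 8 | 0.146 / 0.169 | 0.12 / 0.05 | 0.059 / 0.097 | 0.98 / 0.45 |

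The nominal value is 0.05. Under 'at least half' the error stays near it (4-12%). Under 'all positive' it is 20-98%. A different assumed model (beta-distributed shares, concentration 2 to 8, cut-off 0.5) gives a share gap of 0.08-0.14 rather than 0.15-0.18. The result therefore depends on inputs the documents do not supply.

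**4. Averaging across visits.** If all three scheduled visits were averaged, a deficit of 0.17 present only at 12 months would appear as 0.17/3 = 0.057. A deficit of 0.17 at the first two visits that had resolved by 12 months would appear as 0.34/3 = 0.113, although the 12-month difference is zero. The distortion can go either way.

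**5. Window and margin, side by side.** The window is up to 12 months in one part of SAP 1.2 and 12 ± 2 months in another. SAP 2 and 4.1 have 12 ± 2 months. SAP 7.5 has up to 12 months with ± 2 months added. The margin is 0.17 in the SAP 7.2.1 calculation and in SAP 7.5, and 0.175 in the closing sentence of the SAP 7.2.1 margin argument. Protocol 9.5 treats 0.175 (0.786 − 0.611) as the ceiling and 0.17 as the recommended value below it.

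**The case against.** The strongest reply is that SAP 1.2 sits under a heading about variable names and mentions no margin. SAP 7.5, the analysis section, applies 0.17 to a difference in rates from baseline to 12 months, which is the scale of SAP 7.2.1. This stands in part: the SAP nowhere says that 0.17 will be applied to a mean share. It does not close the gap. SAP 1.2 names the averaged score as primary and carries it through to the comparison of arms, while SAP 7.5 gives no patient-level definition to use instead.

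On visits, the closest-to-12-months rule in SAP 1.2 would remove the conflict if it governs symptoms. It follows the item on revision surgery and spinal deformity, so its reach is arguable. The averaging step also defers to a cited paper that may say what 'across visits' means and how items are coded. What can be said is that the SAP states no rule, not that none exists.

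Three stronger readings are tempting and unsupported:

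- *The trial is underpowered for Aim 2, or 72 is wrong.* The 72 is right for the yes/no endpoint. At equal true means and before clustering, a share with SD 0.41 or less has at least 80% power at 72 per group.
- *The scoring favours PFD.* Under one plausible rule the error stays near nominal, and early and late deficits distort an average over visits in opposite directions.
- *The scoring was chosen with results in view.* SAP 1.2 uses the past tense in a July 2021 document, so scoring may already have been done. Nothing shows that results by arm had been seen.

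**Conclusion.** The point holds and should be fixed. The SAP's primary clinical-improvement score and the quantity behind its margin and sample size are different, and nothing in either document reconciles them. That rests on the text and on the exact reproduction of 72 per group, so confidence is high. Confidence is moderate on averaging over visits, because two readings would remove that conflict: the closest-visit rule, or averaging only repeat visits within one window.

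No size or direction of bias can be stated. The 4-12% and 20-98% figures rest on assumed symptom counts, correlations and responder rules and ignore centre clustering. They show only that an unstated rule can decide the result. Aim 2 is secondary, and the primary outcome (harm) is untouched.

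**What to change.** - **Endpoint.** Make primary clinical improvement one yes/no per patient at the visit closest to 12 months within 10-14 months. State the rule for 'improved', including how stable and never-present items count.
- **Timing of the rule.** Fix it without use of results by arm. If scores by arm have already been seen, say so.
- **Test.** Compare a one-sided 95% limit for the risk difference, accounting for centre, with the single margin of 0.17. Correct the 0.175 in SAP 7.2.1 and use one window throughout.
- **Supportive analyses.** Keep the averaged binary score and the four-level symptom score as supportive, and say whether 'across visits' means within a window.

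**Cost.** This is SAP wording and some re-derivation from data already collected. Patients seen only before 10 months become missing for the primary endpoint. They would be handled under the missing-data plan in SAP 7.5, with an analysis of the closest visit up to 12 months as a sensitivity check. The yes/no outcome is less precise than an averaged score (SD 0.41, against an assumed 0.20-0.35 for a share), but it is the quantity for which 0.17 and 72 per group were set. Which way the result would move is not known in advance.
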